4.2 Primary Safety Endpoint

The primary safety endpoint includes adverse events and device-related adverse events.

Version 2.0 6/30/2021 Page 5 of 13

4.3 Additional Assessments

The following data will be collected on the dialyzer with Endexo during Periods 1 and 2:

- Number and percentage (%) of dialyzers and blood lines for each clotting grade using the visual inspection clotting grade scale
- HD treatment duration or time to complete circuit occlusion (Grade 4)
- Blood volume processed per dialysis session
- The volume, the time of saline administered, and the reason for administration per subject per HD session (other than for circuit priming or rinse back)
- Urea Reduction Ratio (URR) and spKt/V for all HD sessions

5. STATISTICAL METHODS

5.1 General Methodology

There are multiple observations of one measurement for each subject in each period. Unless specified, all analyses will be performed at the subject level, i.e., take average of multiple observations first of the measurement for each subject then analyze/summarize on subject averages.

Descriptive statistics (n, mean, standard deviation, median, minimum, and maximum) will be presented for continuous endpoints. Frequency and percent will be presented for categorical endpoints. Any missing values of an endpoint will not be imputed. All data entered and collected will be listed.

5.2 Analysis Methods for Endpoints

If adequate, 95% confidence interval will be calculated for each dialysis circuits (A) and (B). For comparisons, if adequate, paired-t tests may be performed between dialysis circuits (A) and (B) for continuous endpoints, McNemar's tests may be employed for categorical endpoints.

For 0% heparin, the average of a continuous endpoint from multiple HD treatments will be calculated for each subject, then descriptive statistics will be summarized at subject level.

For β_2 -microglobulin, the laboratory results for post dialysis will be corrected for ultrafiltration using the formula in Bergström and Wehle (1987).

Uncorrected value Corrected value = -----,
$$1 + \Delta W/(0.2PW)$$

Version 2.0 6/30/2021 Page 6 of 13

where ΔW = pre-dialysis weight – post dialysis weight, PW is the post dialysis weight.

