3. CHANGES IN THE CONDUCT OF THE STUDY OR PLANNED ANALYSES

3.1. Changes in the Conduct of the Study

Concurring with FDA's comments/suggestions, the withdrawal criteria when clotting score (CS) = 4 in a HD treatment are as follows:

- If CS=4 in dialyzer, the subject will be withdrawn from the study
- If CS=4 in circuit A bloodline (CombiSet), Period 1, the subject will proceed to washout
- If CS=4 in circuit A bloodline (CombiSet), Period 2, the subject will be withdrawn from the study, and
- If CS=4 in circuit B bloodline (Streamline) in any period, the subject will be withdrawn from the study.

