5.5 Handling of Dropouts or Missing Data

Any missing values at dialysis treatment level of an endpoint will not be imputed.

If a subject missed a HD treatment but was able to have an unplanned HD treatment with the same requirements, the results from the unplanned HD treatment will replace the missed one.

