6.6 Analysis of Primary Endpoint

The frequency for subjects with possible successful heparin-free sessions (0, 1, 2, or 3) will be displayed for each circuit. The descriptive statistics of subject's percent of successful heparin-free sessions will be presented for each dialysis circuits (A) and (B).

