6.7 Analysis of Primary Safety Endpoint

Adverse events will be coded for system organ class and preferred term using Medical Dictionary for Regulatory Activities (MedDRA), Version 23.1. For all AEs and device related AEs, the number and percent of subjects with at least one occurrence, and the number of all occurrences under one preferred term, as well as under one system organ class, will be presented by circuit and % heparin.

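### Does SAP 5.2 need to name the confidence-interval method and the yes/no outcome for McNemar's test?

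*SAP*

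**What the plan says.** The relevant text is spread over several SAP sections.

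- **5.1 (General Methodology)** puts analyses at subject level unless otherwise specified: "take average of multiple observations first of the measurement for each subject then analyze/summarize on subject averages". Continuous endpoints get n, mean, SD, median, minimum and maximum; categorical endpoints get frequency and percent.
- **5.2 (Analysis Methods for Endpoints)** adds the optional items: "If adequate, 95% confidence interval will be calculated for each dialysis circuits (A) and (B"). If adequate, "paired-t tests may be performed between dialysis circuits (A) and (B) for continuous endpoints", and "McNemar's tests may be employed for categorical endpoints". It does not say which endpoint receives the interval, how it is computed, or what adequate means.
- **6.6 (Analysis of Primary Endpoint)** commits to two displays. One is a table: "The frequency for subjects with possible successful heparin-free sessions (0, 1, 2, or 3) will be displayed for each circuit". The other is descriptive statistics of the subject's percent per circuit. It mentions neither an interval nor a test.
- **6.7 (Analysis of Primary Safety Endpoint)** reports "the number and percent of subjects with at least one occurrence", which is a yes/no outcome per subject.

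The Protocol Synopsis (Statistical Methods) also plans only descriptive statistics and the 0–3 frequencies for the primary endpoint.

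**The concern.** Reading 5.1 and 6.6 together, an analyst asked for a 95% interval on the primary endpoint might take the mean of the subject percents and attach a t-interval. Each percent can only be 0, 33.3, 66.7 or 100, and there are only 12 to 16 of them. If the circuits work well, most values sit at 100. The interval can then collapse to a point or run past 100%, and its coverage falls below nominal. High success is the result a feasibility study hopes for, so the weakness would show where precision is of most interest.

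McNemar's test raises a second question. It needs one yes/no pair per subject. The primary endpoint is yes/no only per session; per subject it is a count from 0 to 3. Clotting grade has four levels. No cut-point is given for either, and the choice of cut-point can move the p-value. Because the study is open-label, a choice left until analysis could be made with the results in view.

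**Working it through.** **Inputs.** SAP 2.4 gives 12 to 16 subjects and three heparin-free sessions per circuit. Its session totals reproduce: 12 × 3 = 36 and 16 × 3 = 48. There is no power calculation to reproduce. Neither document gives an expected success rate or a within-subject correlation (ICC), so both are assumed: success 60–95%, ICC 0–0.5.

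**Form of the t-interval.** With k subjects at 2/3 and n − k at 3/3, the mean is 1 − k/(3n) and the variance is k(n − k)/[9n(n − 1)]. The limits are mean ± t(0.975, n − 1) × SD/√n, with t = 2.201 (n=12) and 2.131 (n=16).

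For n=12, k=1: mean = 35/36 = 0.9722; SD/√n = (1/3)/12 = 0.0278; half-width = 2.201 × 0.0278 = 0.0611.

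| Subjects at 2/3 | n=12 | n=16 |
|---|---|---|
| 0 | 100–100% | 100–100% |
| 1 | 91.1–103.3% | 93.5–102.4% |
| 3 | 82.1–101.2% | 86.6–100.9% |
| 4 | upper limit 99.3% | upper limit 99.6% |

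**Coverage.** All 0/1/2/3 configurations were enumerated exactly, with binomial (ICC 0) or beta-binomial (ICC up to 0.5) counts out of three. Ranges run over ICC 0–0.5.

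| True success | Coverage, n=12 | Coverage, n=16 | Zero width, n=12 | Zero width, n=16 |
|---|---|---|---|---|
| 95% | 67–84% | 78–91% | 16–33% | 8–22% |
| 90% | 77–88% | 87–95% | 2–10% | 1–5% |
| 80% | 91–94% | 92–94% | under 1% | under 1% |

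As a check on one cell: at 95% success and ICC 0, a subject has 3/3 with probability 0.95³ = 0.857, and 0.857¹² ≈ 0.158.

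At 60–70% success coverage is 93–96%. At 90% with n=16 it is 95.4% at ICC 0, 94.1% at ICC 0.1 and 87.2% at ICC 0.5, so the shortfall there needs materially correlated sessions. An upper limit above 100% is more common than poor coverage: at 90% success it occurs in 64–84% of trials (n=12) and 40–79% (n=16).

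**The natural alternative.** A Clopper-Pearson interval on the proportion of subjects with 3/3 gives 73.5–100% for 12/12 and 79.4–100% for 16/16. It targets another parameter. With independent sessions, 60% session success corresponds to 0.6³ = 21.6% of subjects with 3/3, and 95% to 0.95³ = 85.7%. Its coverage therefore cannot be set against that of the t-interval as like for like. Pooling sessions as if independent is no answer either: 36/36 gives a lower limit of 90.3%, against 73.5% for 12/12 subjects.

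**McNemar cut-point.** In one constructed set of 12 subjects, a cut at 3 gives five discordant pairs, all in one direction: p = 2 × 0.5⁵ = 0.0625. A cut at 2 gives two: p = 2 × 0.5² = 0.50. A cut at 1 gives none: p = 1.0.

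**The case for a change.** The case for amending is that the gap is real, the arithmetic holds, and a sentence of SAP wording would close it. If the sponsor meant some method other than the t-interval, that is not written down either. Fixing the method and cut-point in advance would remove a choice otherwise open after the data are seen.

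The omission stands, and so do the numbers for the t-interval at high success. The step from there to a defect in the plan is weaker:

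- The t-interval is inferred. Section 5.2 does not tie the interval to the primary endpoint, and since 6.6 displays the counts as categories, a binomial interval is equally open.
- Harm requires an analyst to look at 100–100%, or an upper limit of 103.3%, and judge it adequate. The condition in 5.2 exists to prevent that.
- McNemar's test has a proper use in this study, namely any adverse event per subject (6.7). Nothing in the SAP directs it at the 0–3 count or the clotting grades, for which 6.6 and 6.8 plan distributions and descriptive statistics.
- Replacing the interval with one on 3/3 would score 2/3 the same as 0/3 and leave the stated percent endpoint without an interval. The 3/3 count is already in the 6.6 table, so a reader can compute that interval.

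How subjects withdrawn for clotting (SAP 3.1) or with missing sessions (5.5) are counted is a separate question and does not bear on the interval method.

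**Conclusion.** No change to the plan is called for. SAP 5.2 leaves out the endpoint, method and adequacy criterion for an optional interval, and the outcome for an optional test. The analyses it does commit to, the 0–3 table and descriptive statistics by circuit, are sound as written and show the full distribution. The sample size was not derived from any comparison, and no hypothesis, success threshold or stopping decision uses the interval or the test. The most that is at stake is how precision is reported.

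The t-interval would be a poor choice at about 95% success (coverage 67–84% for n=12, 78–91% for n=16) and, for n=12, at 90% (77–88%). Those figures rest on assumed success rates and ICCs and on a method the SAP does not name. An analyst filling the gap sensibly would report an interval only where it stays within 0–100% and respects three sessions per subject, and would keep McNemar's test for outcomes that are yes/no per subject.

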5.3 Analysis Populations

- Safety Population (SPOP): The SPOP includes subjects who signed the ICF, met inclusion criteria, did not meet any exclusion criteria, were enrolled and randomized in the study.
- **Analysis population (APOP):** The APOP includes subjects who are in the SPOP and have at least one heparin reduction HD treatment in the study.

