3.2. Changes in the Planned Analyses

Concurring with FDA's comments/suggestions, the secondary endpoint of adverse events, and device-related adverse events, became the primary safety endpoint.

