6 STATISTICAL ANALYSES

6.1 Patient Disposition

The subject disposition table will include the items below:

- The number of subjects who signed the informed consent and were screened.
- The number of subjects who failed screening with reasons.
- The number of subjects who were eligible.
- The number of subjects who were randomized.
- The numbers of subjects who completed the following stages: Period 1, Washout, Period 2, and end of study.
- The number of subjects and percent by category of major reasons for early discontinuation.
- The numbers of subjects in the safety and in the analysis populations.

Subject inclusion in the different analysis sets will be listed for all subjects. Subject disposition data will be presented in a listing for all subjects.

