6.2 Protocol Deviations

Any protocol deviation will be listed. Summaries by category of protocol deviations will be presented if the number of protocol deviations is sufficiently large.

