6.9 Analysis of Safety

All safety measurements will be analyzed under the safety population.

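### The Safety Population is defined by eligibility and randomisation rather than exposure, so a dialysed subject later found ineligible drops out of every safety summary table, though not out of the listings.

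*SAP*

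**What the plan says.** SAP 5.3 sets two populations. The Safety Population (SPOP) is defined in these words: "The SPOP includes subjects who signed the ICF, met inclusion criteria, did not meet any exclusion criteria, were enrolled and randomized in the study". The Analysis Population (APOP) is defined in these: "The APOP includes subjects who are in the SPOP and have at least one heparin reduction HD treatment in the study". The APOP is therefore nested in the SPOP.

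SAP 6.9 then states: "All safety measurements will be analyzed under the safety population". Section 6.9.1 sends the reader to 6.7 for adverse events, so the tables in 6.7 fall under the SPOP. These events carry more weight than the protocol first gave them. SAP 3.2 records that they "became the primary safety endpoint", and SAP 4.2 confirms it: "The primary safety endpoint includes adverse events and device-related adverse events".

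The listings are not restricted to a population. SAP 5.1: "All data entered and collected will be listed". SAP 6.1: "Subject inclusion in the different analysis sets will be listed for all subjects". SAP 6.2: "Any protocol deviation will be listed". The Statistical Methods entry of the protocol synopsis also provides a listing of device-related events by circuit.

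**The concern.** A safety set should contain everyone exposed to the device, because a device effect does not depend on whether the subject was properly eligible. This definition goes wrong in two directions.

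- **Exposed but excluded.** A subject dialysed on a study circuit and later found to breach a criterion fails the SPOP definition and leaves the adverse event, laboratory and vital sign tables. Several criteria can come to light late, such as a history of a clotting or bleeding disorder, or use of an anticoagulant. In a heparin-free study, a bleeding or clotting event could itself prompt that discovery, and the rule would then remove the event together with the subject. This is a plausible mechanism. Nothing in the documents shows that it occurred.
- **Unexposed but included.** A subject randomised and never dialysed on a study circuit stays in the SPOP. This lowers event percentages if the SPOP count is the denominator. SAP 6.7 does not say what the denominator is.

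At stake is whether the summary tables for the primary safety endpoint describe the subjects who were treated.

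**Working it through.** **Reading the sections together**

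1. SAP 5.3 lists consent, eligibility, enrolment and randomisation as joint conditions, with no exposure condition.
2. SAP 6.9, through 6.9.1, puts the tables of 6.7 under that set. Section 6.7 names no population of its own.
3. No section provides a summary of all exposed subjects, and the protocol text defines no safety population that could override the SAP.
4. SAP 2.1 places verification of eligibility before randomisation. The problem therefore needs a breach that was missed then and found later.

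**Planning figure**

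SAP 2.4 gives 12 to 16 subjects, three heparin-free sessions per circuit each, and 36 to 48 sessions per circuit. This reproduces: 12 × 3 = 36 and 16 × 3 = 48. One excluded subject removes 1/12 = 8.3% or 1/16 = 6.25% of subjects, and up to 10 study-circuit sessions (5 per circuit).

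**Exposed but excluded (illustration)**

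Assumption: one ineligible dialysed subject has the only device-related event, in a cell that all subjects started.

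| Case | Rule as written | All exposed subjects |
|---|---|---|
| Subject is one of 12 | 0/11 | 1/12 = 8.3% |
| Subject is one of 16 | 0/15 | 1/16 = 6.25% |
| Subject is additional to 12 eligible | 0/12 | 1/13 = 7.7% |
| Subject is additional to 16 eligible | 0/16 | 1/17 = 5.9% |

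The last two rows allow for the protocol's recruitment target being stated in eligible subjects.

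**How likely is at least one such subject?**

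The documents give no rate. With an assumed probability p per subject, independent between subjects, the chance is 1 − (1 − p)^N.

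| Assumed p | N = 12 | N = 16 |
|---|---|---|
| 2% | 21.5% | 27.6% |
| 5% | 46.0% | 56.0% |
| 10% | 71.8% | 81.5% |

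This is the chance that some dialysed subject is dropped. It is not the chance that the dropped subject has the only event.

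**Unexposed but included (only if the SPOP count is the denominator)**

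One never-dialysed subject multiplies event percentages by (N − 1)/N: 11/12 = 0.917 or 15/16 = 0.938. For a single event the loss is 1/11 − 1/12 = 9.09% − 8.33% = 0.76 percentage points, or 1/15 − 1/16 = 6.67% − 6.25% = 0.42 points.

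The same arithmetic applies to later cells, because under SAP 3.1 some subjects may leave before starting them. If k subjects never start a cell, the factor is (N − k)/N. For an assumed k = 3 it is 9/12 = 0.750 or 13/16 = 0.813.

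**The case against.** The strongest reply is that SAP 5.3 simply follows the order of subject flow: consent, screening, enrolment, randomisation. Eligibility is verified before randomisation (SAP 2.1), and no section provides for judging it again afterwards. On that reading the SPOP is everyone who passed screening and was randomised, and nobody drops out later. This may be what was intended, but the SAP does not say so. Section 5.3 states eligibility as a condition in addition to randomisation, and 6.1 counts eligible and randomised subjects separately. If that was the intention, the wording still needs correcting, and an exposure condition would still be missing.

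The second reply is that the listings contain the harm. With so few subjects, a reader can see each event individually, and no decision rule hangs on the percentages. This stands in part: no data are lost, and the effect is confined to the tables. A listing does not, however, restore a missing numerator and denominator in the table for the primary safety endpoint.

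Third, the illustration stacks assumptions: a missed criterion, discovery after dialysis, and the only event falling on that same subject. That is right. If exactly one subject has the event and ineligibility is independent of it, the chance that the event is lost is only the assumed 2% to 10%.

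Fourth, the cell denominator is a reporting gap under any definition of the SPOP, and the dilution figures hold only under a denominator that the SAP does not state. Both remarks are fair, and the conclusion does not rest on them. Where events during the washout are tabulated is also unspecified. That is a separate gap, which this fix does not close.

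**Conclusion.** The concern holds. On its plain wording the SAP drops a dialysed but ineligible subject from every safety summary table, and no summary of all exposed subjects takes its place. The fault in the rule is certain, but its effect depends on whether such a subject exists. The number affected is unknown and possibly zero, and the listings limit the harm to the tables.

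If one such subject exists and had the only device-related event, the table reads zero where the true figure lies between 5.9% (1/17) and 8.3% (1/12). This assumes that every subject started the cell concerned. The point should be corrected, but it does not threaten the study.

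**What to change.** Make three changes of wording in the SAP:

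1. **SPOP (5.3).** All subjects who started at least one study session with the Endexo dialyzer, regardless of eligibility. Flag eligibility breaches in the 6.1 listing of analysis-set membership.
2. **APOP (5.3).** Carry the present consent, eligibility, enrolment and randomisation conditions into the APOP's own definition, alongside at least one heparin-reduction treatment. Every heparin-reduction visit uses the Endexo dialyzer (SAP 2.1), so APOP membership is the same as now. The clotting, saline and spKt/V summaries in 6.8 still leave out, for example, a subject found to be on an anticoagulant.
3. **Denominators (6.7).** For each circuit by heparin-level cell, the denominator is the number of subjects who started at least one session in that cell.

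The cost is three sentences and no new data. There are three downsides. Cell denominators will differ from the SPOP total and need a footnote. The SPOP and APOP will differ in eligibility, which the 6.1 listing must show. Events in a subject randomised but never dialysed on a study circuit will appear only in listings, though such a subject belongs to no circuit by heparin-level cell in any case. If no dialysed subject breached a criterion and every randomised subject was dialysed, SPOP membership does not change.

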2. STUDY DESIGN

2.1. General Description

This is a randomized, open-label, cross-over study with subjects on thrice-weekly (in-center) hemodialysis. The study consists of a Screening Period, study Period 1, Washout Period, study Period 2, and a Follow-up Visit.

• Screening Period:

The Screening Period begins with signing of the informed consent form (ICF) and can extend up to 4 weeks in duration. After completing all required tests/procedures and determining/verifying the eligibility, the subject is randomly assigned to one of the circuit sequences, either AB or BA. The randomization is done in the electronic data capture (EDC) system.

Circuit A consists of the dialyzer with Endexo and CombiSet bloodline and Circuit B consists of the dialyzer with Endexo and Streamline bloodline.

• Period 1:

Period 1 consists of 5 HD sessions (Visits 1 to 5) on the dialyzer with Endexo with the CombiSet bloodline for sequence AB and Streamline bloodline for sequence BA according to the randomization, and different heparin doses shown below:

Visit 1: 100% of heparin as prescribed

Visit 2: 50% of heparin as prescribed

Visits 3, 4, 5: 0% of heparin

This period lasts for approximately two weeks per subject.

Version 2.0 6/30/2021 Page 3 of 13

Washout Period:

The Washout Period occurs between Period 1 and Period 2. It consists of three conventional HD sessions (Visits 6, 7, and 8). This period lasts approximately one week per subject.

• Period 2:

Period 2 consists of 5 HD sessions (Visits 9 to 13) on the dialyzer with Endexo with Streamline bloodline for sequence AB and CombiSet bloodline for sequence BA according to the randomization, and different heparin doses shown below:

Visit 9: 100% of heparin as prescribed,

Visit 10: 50% of heparin as prescribed,

Visits 11, 12, 13: 0% of heparin

• Follow-up Visit:

An in-center Follow-up Visit is to be conducted within 1 week of the subject's last scheduled study HD treatment. This visit cannot be combined with the last study HD visit.

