6.8 Analysis of Additional Assessments

These additional assessments will be analyzed under the analysis population.

- Distributions of clotting scores by circuit, by % heparin will be presented for dialyzer arterial end cap, venous end cap, venous chamber for each bloodline, arterial chamber for Combiset, and arterial pod and venous pod for Streamline.
- For HD delivered, arterial pressure, venous pressure, blood flow rate, dialysate flow rate, HD treatment duration, mean KECN, ultrafiltration volume, and blood volume process, descriptive statistics will be presented by circuit, and % heparin.
- For β_2 -microglobulin, the removal rate {((pre-HD post-HD)/pre-HD) x 100} will be calculated. Descriptive statistics will be presented by circuit, and % heparin for the pre-HD, post-HD and corrected post-HD β_2 -microglobulin concentrations, as well as removal rates from post-HD and corrected post-HD.
- For total volume of saline administered, descriptive statistics will be presented by circuit, and % heparin. Total volume for treating clotting, total volume for treating intradialytic symptoms, and total volume for medication delivery will be presented in the same manner. In addition, the total number of saline flushes and the total number of HD sessions received by subjects will be presented by circuit and % heparin for treating clotting, treating intradialytic symptoms, and for medication delivery.

Version 2.0 6/30/2021 Page 9 of 13

• For URR and spKt/V, descriptive statistics will be presented by circuit, and % heparin.

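### A Grade 4 clot at Visit 1 that triggers withdrawal would be left out of the 100% heparin clotting table, because SAP 6.8 uses a population that requires a later, reduced-heparin session

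*SAP*

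**What the plan says.** Four parts of the SAP act together.

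- **Population for the tables (6.8).** "These additional assessments will be analyzed under the analysis population". The first item is the clotting summary: "Distributions of clotting scores by circuit, by % heparin will be presented for dialyzer arterial end cap, venous end cap", and so on through the bloodline sites. Delivered-dialysis parameters (including treatment duration) and saline volumes follow in the same layout. Each circuit therefore has a 100% heparin row.
- **Membership of that population (5.3).** The APOP consists of safety-population (SPOP) subjects who "have at least one heparin reduction HD treatment in the study".
- **Heparin schedule (2.1).** "Visit 1: 100% of heparin as prescribed", then "Visit 2: 50% of heparin as prescribed". The first session that can qualify a subject for the APOP is Visit 2.
- **Withdrawal after Grade 4 (3.1).** "If CS=4 in dialyzer, the subject will be withdrawn from the study", with no limit by period or circuit. For the Streamline line: "If CS=4 in circuit B bloodline (Streamline) in any period, the subject will be withdrawn from the study". A CombiSet Grade 4 in Period 1 sends the subject to washout instead; in Period 2 it leads to withdrawal.

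The protocol's Appendix II requires thrombus scoring of every dialyzer used, so a Visit 1 score will exist. SAP 6.9 puts safety measurements on the SPOP, but its subsections cover adverse events, laboratory tests, vital signs and physical findings. Clotting scores are not among them.

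**The concern.** Entry to the clotting table can depend on the outcome that the table reports. A withdrawal-triggering Grade 4 at Visit 1 prevents the subject from reaching a reduced-heparin session, and without that session the Grade 4 is not counted. This is not missing data: the score has been recorded, and the population rule sets it aside.

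Two consequences follow if such an event occurs. The circuit's 100% row, which is the within-study reference for the 50% and 0% rows, would understate Grade 4 clotting. The two bloodlines would also be treated differently: a Visit 1 Grade 4 in the CombiSet line would normally be counted against Circuit A, while the same grade in the Streamline line would not be counted against Circuit B. The duration and saline summaries would lose the same session.

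**Working it through.** **The plan's own size figure.** SAP 2.4 gives 12 to 16 subjects with three heparin-free sessions per circuit: 12 × 3 = 36 and 16 × 3 = 48, matching its 36 to 48 sessions per circuit. There is no formal sample size calculation, margin or power figure to reproduce.

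**Tracing the rules.** The rules of SAP 3.1 and 5.3, applied to a first Grade 4 event at a given visit:

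| First Grade 4 | Sequence AB | Sequence BA |
|---|---|---|
| Visit 1 (100%), dialyzer | Withdrawn, **not in APOP** | Withdrawn, **not in APOP** |
| Visit 1 (100%), bloodline | CombiSet: to washout, enters APOP on reaching Visit 10 | Streamline: withdrawn, **not in APOP** |
| Visit 2 or later in Period 1 | In APOP | In APOP |
| Visit 9 (100%), any site | In APOP if a reduced session was held in Period 1 | In APOP if a reduced session was held in Period 1 |
| Visit 10 or later | In APOP | In APOP |

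Exactly three routes lose the event, all at Visit 1.

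**Effect of one event.** Assume one subject is withdrawn by one of these routes, every other planned subject contributes one 100% session on that circuit (in Period 1 or Period 2), and there is no other Grade 4. The SAP's layout is by circuit and heparin level, pooled over periods. Intervals are exact (Clopper-Pearson) 95%.

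| Planned N | Row as planned (APOP) | Row with all treated subjects |
|---|---|---|
| 12 | 0/11 = 0% (0 to 28.5%) | 1/12 = 8.3% (0.2 to 38.5%) |
| 16 | 0/15 = 0% (0 to 21.8%) | 1/16 = 6.3% (0.2 to 30.2%) |

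**How likely is such an event?** The documents give no rate of Grade 4 clotting at full heparin, so the per-subject probability p at Visit 1 is an assumption. The chance of at least one event among N subjects is 1 − (1 − p)^N.

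| Assumed p | N = 12 | N = 16 |
|---|---|---|
| 0.1% | 1 − 0.999^12 = 1.2% | 1 − 0.999^16 = 1.6% |
| 0.5% | 1 − 0.995^12 = 5.8% | 1 − 0.995^16 = 7.7% |
| 1% | 1 − 0.99^12 = 11.4% | 1 − 0.99^16 = 14.9% |
| 2% | 1 − 0.98^12 = 21.5% | 1 − 0.98^16 = 27.6% |

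**The case against.** The case for leaving the plan alone has several parts.

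- **The contingency is narrow.** The event must occur at the first session, under the subject's full usual heparin, in a population selected for a working fistula or graft, spKt/V of at least 1.2, a stable heparin prescription and no history of clotting disorders. This stands. A reader might infer that the 100% row is biased as a matter of course. The documents do not support that: the row is affected only if such an event happens, and nothing in them favours one assumed rate over another.
- **The event would not vanish from the report.** A reader might infer that it would. But SAP 5.1 lists all data, SAP 6.1 tabulates reasons for early discontinuation, and SAP 6.7 with 6.9 tabulates adverse events by circuit and heparin level in the SPOP. That last route is the primary safety endpoint, although the documents do not say that every Grade 4 must be recorded as an adverse event. This also stands. It leaves the clotting summary showing zero when one event occurred.
- **The table is secondary.** Clotting grades are an additional assessment, and no hypothesis or decision rule rests on the 100% row. A reader might infer that the primary endpoint is affected. It is not, because it counts heparin-free sessions only.
- **The restriction can be defended.** It keeps the 100% row to subjects who also have reduced-heparin data. The SAP does not give this reason, and the argument does not answer the dependence on outcome or the unequal handling of the two bloodlines.

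**Conclusion.** The point holds as a conditional flaw in a descriptive table. As written, SAP 2.1, 3.1, 5.3 and 6.8 together remove a withdrawal-triggering Visit 1 Grade 4 from its circuit's 100% heparin row, and no planned clotting summary on another population restores it. With 12 to 16 subjects, one such event is the difference between 0% and 6.3% to 8.3%, provided every other subject contributes a 100% session on that circuit. Whether any such event arises cannot be judged from the documents. The primary endpoint and the adverse event tables do not depend on this rule. The change is still worth making, because the exclusion selects on the tabulated outcome and is simple to remove.

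**What to change.** In SAP 6.8, present the tables by heparin level of clotting scores, treatment duration, saline and delivered-dialysis data for all randomized subjects with at least one HD session on a study circuit, using every session received. Keep the APOP for summaries limited to reduced or 0% heparin. The withdrawal rules in SAP 3.1 are not touched.

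The cost is one sentence in the SAP and no new data. The downside is that the 100% row may include a few subjects with no reduced-heparin data, which a footnote with their number can make clear. If no subject leaves before a reduced-heparin session, the tables do not change. A smaller alternative is to keep the APOP tables and repeat the clotting table on the SPOP, which would restore the Grade 4 count but not the duration and saline data from the same session.
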